Study Protocol with Statistical Analysis Plan

Official Title:

Effectiveness of Augmented Reality as a Distraction Technique for Reducing Pain and Anxiety in Pediatric Dental Extractions: A Parallel-Group, Double-Blind Randomized Controlled Trial

NCT Number: NCT06954883

Unique Protocol ID: 17-2024-0004

Document Date: April 30, 2025

Author: [name]

Institution: Faculty of Dentistry, Assiut University Dental Hospital

1. Administrative Information

Principal Investigator: [name]

Institution: Faculty of Dentistry, Assiut University Dental Hospital

Trial Registration: ClinicalTrials.gov (NCT06954883)

Unique Protocol ID: 17-2024-0004

2. Background and Rationale

Pediatric dental anxiety and pain are common barriers to care.

Augmented Reality (AR) may reduce distress by immersive distraction.

Hypothesis: AR distraction will reduce pain and anxiety vs. Tell–Show–Do.

3. Objectives

Primary: To evaluate the effect of AR distraction on pain (Wong-Baker FACES).

Secondary: To evaluate effect on anxiety (CFSS-DS) and heart rate.

4. Study Design

Randomized, controlled, parallel-group, single-blind trial.

Setting: Pediatric Dentistry Clinic, Assiut University Dental Hospital.

5. Participants

Eligibility: Children aged 6–10 years, requiring tooth extraction, ASA I.

Exclusion: Visual/hearing impairment, neurological disorders, traumatic dental history.

6. Interventions

AR group: 30 children wore AR headset during anesthesia and extraction.

Control group: 30 children received Tell–Show–Do technique.

7. Outcomes

Primary: Pain (Wong-Baker FACES, 0–10).

Secondary: Anxiety (CFSS-DS, 15–75), Heart rate (bpm).

8. Sample Size Calculation

Based on 2-point difference in Wong-Baker scale, power 80%, alpha=0.05.

25 per group needed, increased to 30 per group (N=60).

9. Randomization and Blinding

Block randomization, sealed envelopes for allocation concealment.

Outcome assessors blinded to group allocation.

10. Statistical Analysis Plan

Analysis: Intention-to-treat. Significance $p<0.05$, two-sided.

Continuous data: Mean \pm SD, compared with t-tests (independent/paired).

Effect size (Cohen's d) calculated. Missing data <5% complete case.

Secondary outcomes analyzed similarly. Sensitivity analysis: per-protocol.

11. Ethics and Dissemination

Approved by Institutional Review Board, informed consent obtained.

Trial conducted per Declaration of Helsinki. Results to be published.

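### Does the missing-data rule in Section 10 need a method for 3 or more missing scores and a sensitivity analysis that varies them?

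*Combined protocol and SAP*

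**What the plan says.** Section 10 plans an intention-to-treat analysis with independent and paired t-tests at a two-sided 5% level. On missing data it says only "Missing data <5% complete case". It continues: "Secondary outcomes analyzed similarly. Sensitivity analysis: per-protocol". CFSS-DS anxiety and heart rate therefore inherit whatever rule applies to the Wong-Baker pain score.

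No section mentions imputation, bounds or a tipping-point analysis, or gives an expected rate of loss. Section 8 gives the design basis as "Based on 2-point difference in Wong-Baker scale, power 80%, alpha=0.05", arrives at 25 per group and raises this to 30, without stating an SD or a reason for the increase. Section 6 describes the intervention in the past tense: "AR group: 30 children wore AR headset during anesthesia and extraction", with 30 controls described likewise.

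**The concern.** Read as a conditional rule, the phrase sets a limit and stops there. With 60 children a strict limit of under 5% is reached at the third missing score. From that point the plan names no method, so the choice could be made after the data are seen. The denominator is also unstated: per arm, 1 of 30 (3.3%) qualifies and 2 of 30 (6.7%) does not. Paired tests need two values per child, so 2 missing at each of two time points could remove 4 of 60 pairs (6.7%) if different children are affected.

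The per-protocol analysis does not fill the gap. It changes which children are counted, not what is assumed about those without a score. If a poor method were chosen, or if the children lost differed in pain from those kept, a result close to p = 0.05 would have no planned check.

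**Working it through.** **Inputs.** From Section 8: 30 per group (60 in all), 25 per group before the increase, a 2-point difference, 80% power, alpha 0.05. From Section 10: two-sided testing. The SD is not stated, so it is an assumption.

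**1. The plan's own figure.** The 25 per group cannot be reproduced without an SD. Solving two-sided t-test power = 0.80 at n = 25 per group gives a standardised difference of 0.8087, so SD = 2/0.8087 = 2.473. The range examined is 2.0 to 3.0.

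**2. The limit.** 2/60 = 3.3% is below 5%; 3/60 = 5.0% is not. The count of at most 2 is right if the percentage is taken per outcome over all 60 children.

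**3. Power lost under complete case** (difference 2):

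| Children analysed | SD 2.0 | SD 2.473 | SD 3.0 |
|---|---|---|---|
| 30 v 30 | 96.8% | 86.9% | 71.9% |
| 28 v 30 | 96.2% | 85.6% | 70.3% |
| 27 v 30 | 95.9% | 85.0% | 69.5% |
| 25 v 25 | 93.4% | 80.0% | 63.7% |

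Three losses in one arm cost about 2 points of power. At SD 2.473, even 10 losses split equally leave the 80% that was planned.

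**4. Could missing scores overturn a positive result?** Put all k losses in the AR arm and keep the complete-case standard error. The smallest significant difference is t(0.975, df) × SD × √(1/(30−k) + 1/30), with df = 58 − k.

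- k = 2, SD 2.473: 2.003 × 2.473 × 0.2628 = 1.302.
- k = 3, SD 2.473: 2.004 × 2.473 × 0.2653 = 1.315.

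If the missing AR children score s points above the observed AR mean, the difference falls by s × k/30. The shift that removes significance from an observed 2-point difference is (2 − critical difference) × 30/k:

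| SD | k = 2 | k = 3 |
|---|---|---|
| 2.0 | 14.2 | 9.4 |
| 2.473 | 10.5 | 6.9 |
| 3.0 | 6.3 | 4.05 |

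On a 0–10 scale the values above 10 are impossible and most of the others implausible. With s = 4 and SD 2.473, only observed differences of 1.30 to 1.57 (k = 2, adding 4 × 2/30 = 0.267) or 1.31 to 1.71 (k = 3, adding 4 × 3/30 = 0.400) would lose significance.

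**5. Loss in the other direction.** Suppose the true difference is 2 and the missing control children lie 2 to 4 points above the observed control mean. The expected observed difference is then 2 − s × k/30. At SD 2.473 power falls from 85.6% to between 80.6% and 74.6% (k = 2), and from 85.0% to between 76.9% and 66.9% (k = 3). This works against finding a benefit; it does not create a false one. Equal loss with equal excess in both arms gives no bias.

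**6. What a poor choice of method would do.** Filling 3 missing scores in one arm with that arm's mean, and testing them as observed, inflates t by √((58/55) × (1/27 + 1/30)/(2/30)) = 1.055. Type I error becomes 6.3% instead of 5.0%. With 3 filled per arm it is 7.8%. The plan proposes nothing of the kind; complete case holds 5.0% when loss is unrelated to pain.

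**The case for a change.** The strongest case for a change is that the text does stop short. On either reading, no fallback is stated once 3 scores are missing, and three is not a remote count if loss is more than trivial. The chance of 3 or more missing of 60 is 0.12 at an assumed loss rate of 2%, 0.27 at 3% and 0.58 at 5%. An intention-to-treat claim sits awkwardly beside silence about randomised children without scores, and a sentence in the SAP costs almost nothing.

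The omission stands as a matter of wording. Its consequence does not. Those loss rates are assumptions; the documents describe a single procedure, mention no follow-up visit and describe 30 treated children in each arm. The inflated type I error needs a method nobody has proposed. The paired-loss figure needs two time points and losses in different children, and the plan gives no assessment times.

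A planned tipping-point analysis would add little. Raising missing AR scores by up to 4 points could not overturn a 2-point result with 2 or 3 missing anywhere in the SD range (smallest shift needed 4.05). A version that moves only AR scores would also miss control-arm loss, the larger effect above. Any choice of shifts would be a matter of taste, since the documents give no basis for one. A borderline result remains open to question, but an analyst can examine that when reporting it.

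**Conclusion.** No change to the plan is called for. The phrase in Section 10 can mean a rule limited to under 5% missing, or an expectation of under 5% with complete case as the method. Under both, complete case is the only method named, and an analyst facing 3 or 4 missing scores would sensibly keep it and report the numbers and reasons by arm, as ordinary trial reporting does. Spelling that out would leave the primary analysis as it is.

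Nothing the plan states is shown to give a wrong result. At SD 2.473 the cost of 3 losses in one arm is 86.9% − 85.0% = 1.9 points of power, and a result at the 2-point target is out of reach of any plausible pattern of 2 or 3 missing scores. The least comfortable case is SD 3.0 with all 3 losses in AR, where each missing child would have to score about 4 points above the AR mean.

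This conclusion rests on an SD between 2.0 and 3.0, which the plan does not state, and on loss staying at a few children, which the single-procedure design suggests but the documents do not quantify. Confidence is moderate because the wording is ambiguous. Substantial or clearly one-sided loss would need discussion in the report, with any added analysis labelled post hoc if the data had already been analysed.
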